9.1.7.2 Additional Laboratory Assessments

For any safety event or laboratory abnormality, additional laboratory assessments, imaging, and consultation may be performed for clinical evaluation and/or in consultation with the study Medical Monitor; results may be collected and should be included in the clinical database.

For patients undergoing cholecystectomy due to cholecystitis, cholelithiasis or any other biliary pathology, the following should be performed, as possible: histopathological evaluation of the resected gallbladder and analyses of gallbladder contents including bile and gallstone composition. If performed, results should be included in the SAE and/or AESI report, as applicable.

Additional laboratory assessments will be performed in patients who experience any LFT abnormalities as outlined in Section 6.5.1.1. Following the occurrence of elevated liver transaminases or other LFT abnormalities per central laboratory, all assessments in Table 11 will be performed, as well as hematology, biochemistry, LFT, and coagulation assessments from Table 10, AT levels, and other assessments or evaluations per Investigator discretion, as appropriate.

Monitoring and dose modification will also be performed as outlined in Section 6.5.1.1.

Table 11: Hepatic Assessments in Patients who Experience LFT Elevations

Extended Hepatic Panel			
Herpes Simplex Virus 1 and 2 antibody IgM, IgG	Herpes Zoster Virus IgM, IgG		
HIV 1 and 2 ^a	HHV-6		
Cytomegalovirus antibodies, IgM, IgG	HBsAg, HBc antibody IgM and IgG		
Anti-nuclear antibodies	Epstein-Barr Virus antibodies, IgM and IgG		
Anti-smooth muscle antibodies Anti-mitochondrial antibodies			
HCV antibody	HAV antibody IgM		
HCV RNA PCR – qualitative and quantitative	HEV antibody IgM		
Imaging			
Abdominal ultrasound with Doppler flow (or CT or MRI) including right upper quadrant			
Focused Medical and Travel History			
Use of any potentially hepatotoxic concomitant medications, including over the counter medications and herbal remedies	Alcohol consumption		
Other potentially hepatotoxic agents including any work-related exposures	Recent travels to areas where hepatitis A or E is endemic		

Abbreviations: CT=computed tomography; HAV=hepatitis A virus; HBc=hepatitis B core; HBsAg=hepatitis B virus surface antigen; HCV=hepatitis C virus; HEV=hepatitis E virus; HHV-6=human herpesvirus 6; HIV=human immunodeficiency virus; IgG=immunoglobulin G antibody; IgM=immunoglobulin M antibody; MRI=magnetic resonance imagery; PCR=polymerase chain reaction; PT=prothrombin time; RNA=ribonucleic acid

9.1.7.3 Urinalysis

Urine samples will be collected as specified in the Schedule of Assessments (Table 1, Table 2 and Table 3) for evaluation of the following urinallysis parameters:

Table 12: Urinalysis Parameters

Urinalysis ^{a, b}	
Leukocytes	Red blood cells
Protein	pH (dipstick)
Bilirubin	Nitrite
Urobilinogen	Specific gravity
Ketone	Glucose

a Visual or automated inspection for appearance and color will occur.

a HIV testing will not be performed where prohibited by local regulations.

b Urine microscopy will be performed if clinically indicated.

9.1.7.4 Antidrug Antibodies

To explore the effect of fitusiran on the induction of antidrug antibodies, blood samples will be collected as specified in the Schedule of Assessments (Table 1, Table 2 and Table 3).

Details regarding the processing, shipping, and analysis of the samples will be provided in the Laboratory Manual.

9.1.8 Inhibitor Status

Patients inhibitor status will be determined as specified in the Schedule of Assessments (Table 1, Table 2 and Table 3) by Nijmegen modified Bethesda assay.

9.1.9 FibroScan or FibroTest and APRI

FibroScan will be performed at the clinical study center according to the Schedule of Assessments (Table 1, Table 2 and Table 3) to determine cirrhosis status in patients with a history of hepatitis C. If FibroScan is unavailable, FibroTest and APRI will be performed at the central laboratory according to the Schedule of Assessments (Table 1, Table 2 and Table 3).

9.2 ADVERSE AND SERIOUS ADVERSE EVENTS

9.2.1 Adverse Event Definition

An AE is any untoward medical occurrence in a patient or clinical investigational subject administered a pharmaceutical product and which does not necessarily have a causal relationship with this treatment.

An AE can therefore be any unfavorable and unintended sign (including an abnormal laboratory finding, for example), symptom, or disease temporally associated with the use of a medicinal product, whether or not considered related to the medicinal product.

Bleeding events will not be recorded as AEs but will be recorded on a separate bleeding events page of the eCRF. Data will be captured to classify whether bleeding events are related to hemophilia and whether they are spontaneous or traumatic.

Any medical condition that is present when a patient is screened and does not deteriorate should not be reported as an AE; however, if the medical condition does deteriorate at any time after administration of the first dose of study drug, it should be reported as an AE.

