2 STUDY OBJECTIVES

2.1 PRIMARY OBJECTIVE

The primary objective of this study is to evaluate the long-term safety and tolerability of fitusiran in male patients with moderate or severe hemophilia A or B.

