8 ASSESSMENT OF EFFICACY

8.1 ASSESSMENT OF BLEEDING EVENTS AND ADMINISTRATION OF FACTOR OR BYPASSING AGENT USAGE

Patients will be provided take home diaries. Patients will be trained to complete the diaries on an ongoing basis to record episodes of bleeding, administration of factor or BPA, as applicable, and response to factor or BPA treatment. Details will be recorded as specified in the Schedule of Assessments (Table 1, Table 2 and Table 3). Data recorded in the diaries will be reviewed with the clinical study center staff or home healthcare professional.

Bleeding Episode Definitions

A bleeding episode is defined as any occurrence of hemorrhage that requires administration of factor concentrates or BPA infusion, eg, hemarthrosis, muscle, or mucosal bleeding episodes. Since bleeding episodes are recorded as an efficacy assessment of fitusiran, these will not be treated as AEs unless they meet any of the SAE criteria listed in Section 9.2.2.

The definition of bleeding episode types described below is based on consensus opinion of International Society on Thrombosis and Haemostasis (ISTH) as reflected in a recent publication (18).

The start time of a bleeding episode will be considered the time at which symptoms of a bleeding episode first develop. Bleeding, or any symptoms of bleeding at the same location, that occurs within 72 hours of the last injection used to treat a bleeding episode at that location will be considered a part of the original bleeding event, and will count as one bleeding episode towards the ABR. Any bleeding symptoms that begin more than 72 hours from the last injection used to treat a bleeding episode at that location will constitute a new bleeding event.

A spontaneous bleeding episode is a bleeding event that occurs for no apparent or known reason, particularly into the joints, muscles, and soft tissues.

A joint bleeding episode is characterized by an unusual sensation in the joint ("aura") in combination with 1) increasing swelling or warmth over the skin over the joint, 2) increasing pain or 3) progressive loss of range of motion or difficulty in using the limb as compared with baseline.

A muscle bleed may be characterized by pain, swelling and loss of movement over the affected muscle group.

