9.2.2 Serious Adverse Event Definition

An SAE is any untoward medical occurrence that at any dose:

• Results in death

- Is life-threatening (an event which places the patient at immediate risk of death from the event as it occurred. It does not include an event that had it occurred in a more severe form might have caused death)
- Requires inpatient hospitalization or prolongation of existing hospitalization
- Results in persistent or significant disability or incapacity
- Is a congenital abnormality or birth defect
- An important medical event that may not be immediately life-threatening or result in death or hospitalization but may jeopardize the patient and may require intervention to prevent one of the other outcomes listed in the definition above (eg, events include allergic bronchospasm requiring intensive treatment in an emergency room or at home, blood dyscrasias, convulsions, or the development of drug dependency or abuse).

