9.2.9 Serious Adverse Event and Adverse Events of Special Interest Reporting

An assessment of the seriousness of each AE will be made by the Investigator. Any AE and laboratory abnormality that meets the SAE criteria in Section 9.2.2 and any AESI must be reported to the CRO within 24 hours from the time that clinical study site personnel first learn of the event. All SAEs and AESI must be reported regardless of the relationship to study drug.

The initial report of SAEs should include at least the following information:

- Patient's study number
- Description and date of onset of the event
- Criterion for serious
- Preliminary assignment of causality to study drug

To report the SAE or an AESI, complete the SAE/AESI form.

Within 24 hours of receipt of relevant follow-up information, the Investigator must update the SAE/AESI form. SAE/AESI forms must be reported using the contact information provided below.

SAE Reporting Contact Information

PSI CRO

[contact]

Appropriate remedial measures should be taken by the Investigator using his/her best medical judgment to treat the SAE. These measures and the patient's response to these measures should be recorded. All SAEs, regardless of relationship to study drug, will be followed by the Investigator until satisfactory resolution or the Investigator deems the SAE to be chronic or stable. Clinical, laboratory, and diagnostic measures should be employed by the Investigator as needed to adequately determine the etiology of the event.

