2 STUDY OVERVIEW

2.1 SYNOPSIS OF STUDY DESIGN

LTE14762 is an open-label extension (OLE) study to evaluate long-term safety, tolerability, and efficacy of subcutaneously administered fitusiran in patients with moderate or severe hemophilia A or B, with or without inhibitory antibodies to factor VIII or factor IX, who previously tolerated dosing in the parent study, TDR14767(formerly ALN-AT3SC-001). The primary objective of this study is to evaluate the long-term safety and tolerability of fitusiran, assessed by incidence, severity, relatedness, and seriousness of adverse events, and laboratory assessments.

TDR14767(ALN-AT3SC-001) was a Phase 1 study that evaluated the safety, tolerability, and PK of fitusiran in healthy male volunteers and male patients with hemophilia A or B.

TDR14767(ALN-AT3SC-001) was conducted in 4 parts:

Part A: a randomized, placebo-controlled, single-blind single-ascending dose (SAD) phase in healthy subjects

Part B: an open-label, multiple-ascending dose (MAD) phase in patients with moderate to severe hemophilia A or B without inhibitors

Part C: an open-label, exploratory multiple dose (MD) phase in patients with moderate to severe hemophilia A or B without inhibitors

Part D, an open-label MD phase in patients with moderate to severe hemophilia A or B with inhibitors.

Study TDR14767(ALN-AT3SC-001) was completed on 20 July 2017 (last patient last visit).

Patients who received all 3 doses of study drug in TDR14767(ALN-AT3SC-001) and completed required study visits in the parent study were eligible for participation in LTE14762. All enrolled participants will initially receive a 50 mg or 80 mg dose of fitusiran once monthly.

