6.8.2 Adverse events

Adverse events (AE) analysis will include treatment-emergent events, with onset occurring in the LTE14762 study. (Note: All AEs collected in LTE14762 are considered TEAE because all participants received dose in TDR14767(ALN-AT3SC-001).)

All AEs will be coded using the MedDRA(version 25.1 or later) coding system and displayed in tables and data listings using system organ class (SOC) and preferred term (PT). AEs will be summarized by the numbers and percentages of participants reporting at least 1 AE, having at least 1 AE by primary SOC and PT. A participant with multiple occurrences of an AE will be counted only once in the respective AE category. Participants who report multiple occurrences of the same AE (preferred term) will be classified according to the most related or most severe occurrence, respectively.

All AE summaries will be summarized (frequency counts and percentages) by system organ class and/or preferred term, unless specified otherwise. The SOC will be presented according to

international standards (MedDRA Internationally Agreed Order), and the preferred term will be sorted within each SOC in decreasing order of frequency.

The following events are considered to be AEs of special interest (AESI):

1. ALT or AST elevations $>3 \times$ ULN
2. Suspected or confirmed thromboembolic events
3. Severe or serious injection site reactions (ISRs), ISRs that are associated with a recall phenomenon (reaction at the site of a prior injection with subsequent injections) or, those that lead to temporary dose interruption or permanent discontinuation of study drug.
4. Systemic (injection associated reactions (IARs), defined as hypersensitivity reactions which are related or possibly related to IMP.
5. Cholecystitis
6. Cholelithiasis

The identification of cholecystitis and cholelithiasis will be a combination of systematic search of higher level group term (HLGT) and AESI collected as it is in CRF. AEs whose HLT fall into the categories listed below will be considered as AESI of cholecystitis and cholelithiasis:

1. Bile duct disorders,
2. Gallbladder disorders
3. Hepatic and hepatobiliary disorders

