An overall summary of TEAEs will include the number and percentage of participants with any TEAE, any TEAE assessed by the Investigator as related to study drug (possibly related or definitely related), any serious TEAE (TESAE), any TESAE related to study drug, any TEAE of special interest; any AE/SAE leading to permanent study drug discontinuation, any TEAE/TESAE leading to study withdrawal, and any deaths. The TEAE onset within any major surgery period will be provided in a separate column in the overview summary statistics as well as in the overall column. They will be excluded from the rest of by-indication columns in the table.

Tabulations of TEAEs by SOC and PT excluding those AE onsets within major surgery period will be produced for the following:

1. TEAEs
2. TEAEs by severity
3. Treatment emergent SAEs
4. TEAEs related to study drug
5. Treatment emergent SAEs related to study drug
6. TEAEs leading to permanent study drug discontinuation
7. Treatment emergent SAEs leading to permanent study drug discontinuation
8. TEAEs leading to study withdrawal
9. Treatment emergent SAEs leading to study withdrawal
10. Treatment emergent AESI (Adverse Events of Special Interest)
11. TEAEs potentially consistent with Covid-19. These AEs will be identified based on SMQ group searching.

All AEs will be listed along with the information collected on those AEs, eg, AE relationship to study drug, AE outcome etc. By-participant listings will also be provided for the following: all participant deaths, all SAEs, and all AEs leading to permanent study drug discontinuation or study withdrawal, all AEs leading to death. AE onset during the major surgery period will also be included in each of the by-participant listing with major surgery flag.

The incidence rate of severe or serious ISRs will also be summarized. The incidence rate is defined as the number of severe or serious ISRs per study drug injection. If multiple ISRs occur between two consecutive injections, they will be counted under the first injection as 1 ISR.

Because of hepatitis C infected participant got enrolled in the TDR14767(ALN-AT3SC-001) study, participants with treatment emergent ALT or AST elevations > 3 ULN AESI will be analyzed based on their HCV status at the enrollment of LTE14762 study.

Additional summary of incidence rate for TEAE, SAE, AEs leading to permanent study drug discontinuation and AESI before and after the 2020 dose pause by primary SOC and PT will be provided.

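### Protocol 9.2.1 keeps all bleeds out of the AE record while 8.1 excepts bleeds that meet an SAE criterion, so a non-fatal serious bleed could be missing from the SAE data

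*Protocol*

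**What the plan says.** Protocol 9.2.1, which defines an AE, says: "Bleeding events will not be recorded as AEs but will be recorded on a separate bleeding events page of the eCRF". It has no exception for serious bleeds and no pointer to 8.1.

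Protocol 8.1 explains that bleeding episodes are efficacy data and then says: "these will not be treated as AEs unless they meet any of the SAE criteria listed in Section 9.2.2".

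Protocol 9.2.2 opens with "An SAE is any untoward medical occurrence that at any dose" and lists the usual seriousness criteria. It does not mention bleeds in either direction.

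Protocol 9.2.9 sets the reporting duty, with a 24-hour limit: "Any AE and laboratory abnormality that meets the SAE criteria in Section 9.2.2 and any AESI must be reported to the CRO". The AESI list in 9.2.7 covers transaminase elevations, thrombosis, certain injection site reactions, systemic injection reactions, cholecystitis and cholelithiasis. Bleeding is not on it.

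On the analysis side, Protocol 2.1 says "The primary objective of this study is to evaluate the long-term safety and tolerability of fitusiran". SAP 2.1 adds that this is "assessed by incidence, severity, relatedness, and seriousness of adverse events, and laboratory assessments". SAP 6.8.2 then says: "Adverse events (AE) analysis will include treatment-emergent events, with onset occurring in the LTE14762 study". Its serious-event tables are subsets of those AEs. Neither document describes a step that brings serious events from the bleeding page into these tables.

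**The concern.** The two protocol sections give different answers to one practical question: does a bleed that puts a patient in hospital or threatens his life get an AE/SAE entry? Site staff deciding what counts as an AE will naturally look in 9.2.1. The exception is in the efficacy chapter.

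Safety is the primary objective, and it is judged by the incidence and seriousness of AEs. In a hemophilia trial with dose reductions and two program-wide interruptions (2017 and 2020), serious bleeding is a harm that readers will look for. If sites resolve the conflict differently, SAE counts depend partly on which section a site followed. That would also affect the comparison of event rates before and after the 2020 pause planned in SAP 6.8.2.

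**Working it through.** The documents give no figure on this point, so there is nothing to reproduce. The check is to follow one event, a non-fatal bleed that leads to hospitalization, through the text.

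| Step | Site follows 8.1 | Site follows 9.2.1 literally |
|---|---|---|
| Entered on the bleeding page | Yes | Yes |
| Recorded as an AE | Yes, because it meets a 9.2.2 criterion | No |
| 24-hour report under 9.2.9 | Yes, as a serious AE | Not clearly triggered: not recorded as an AE, not a laboratory abnormality, not an AESI |
| In the SAP 6.8.2 SAE tables | Yes | No |
| In the bleeding analyses of SAP 6.3 | Eligible | Eligible |

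Three further points follow from the text.

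1. **9.2.2 only partly repairs the conflict.** Its definition is wide enough to include a serious bleed, and a site that reads it literally would report one. But it does not override the specific instruction in the section before it, and 9.2.9 begins from events already classed as AEs.
2. **The two rules differ in scope.** Section 8.1 limits a bleeding episode to hemorrhage needing factor or bypassing agent. Section 9.2.1 speaks of bleeding events without that limit and provides for classifying whether they are related to hemophilia. A serious hemorrhage managed without factor could fall under the 9.2.1 exclusion but outside the 8.1 exception.
3. **The bleeding analyses do not stand in for the SAE record.** The annualized bleeding rate in SAP 6.3.1.1 counts bleeds without regard to seriousness or relatedness, and the primary on-treatment version leaves out interruption and perioperative periods.

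**Scale.** SAP 6.8.2 counts a participant once per AE category, so a missed bleed changes participant-level SAE incidence only if that participant has no other recorded SAE. The planned maximum is 48 patients (Protocol 3.2). If all 48 are in the safety set:

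- change in SAE incidence per such participant = 1/48 = 0.0208, or about 2.1 percentage points.

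SAP 4 and 5.2 split the analysis into two safety sets and tabulate by hemophilia type and inhibitor type. The documents do not give the sizes of those groups. With an assumed denominator of 30, the same event is worth 1/30 = 3.3 points.

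**The case against.** The strongest reply is that the protocol, read as a whole, already contains the right rule. Section 9.2.1 is the general statement, 8.1 is the specific exception, and the exception points into the safety chapter. Section 9.2.2 covers any untoward occurrence that meets a criterion, and 9.2.3 has sites ask about hospitalization, so a bleed leading to admission should come to light. Diaries and bleed management are reviewed at each dosing and every two weeks in between. The eCRF completion guidelines and the SAE/AESI form are not among the documents and may already carry the exception.

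Much of this stands. A reader might infer that a site following 9.2.1 would necessarily send no SAE report, or that serious bleeds vanish from the trial. The documents support neither reading. The SAE definition does not exclude bleeds, so a missed report is possible but not certain. The bleed stays on the bleeding page. SAP 6.3 analyses all bleeds, treated and untreated, alongside the primary treated-bleed analysis. SAP 6.3.3 summarizes factor use by bleed severity, and SAP 6.5 reports bleeding rates during both interruptions. Fatal bleeds have a separate route, since SAP 6.8.2 promises: "By-participant listings will also be provided for the following: all participant deaths, all SAEs".

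What the reply does not remove is the unqualified sentence in 9.2.1, the AE-based trigger in 9.2.9, and the lack of any planned step linking the bleeding page to the SAE tables.

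**Conclusion.** This is an internal inconsistency in current text, and it touches the primary-objective data. Followed literally, 9.2.1 leaves a non-fatal serious bleed without an AE record. The event could then miss both the 24-hour report and the SAP 6.8.2 tables, and SAE incidence would be incomplete.

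The size cannot be known from the documents, because they do not say how many serious bleeds occurred or how sites recorded them. The figure of about 2.1 points per participant is for scale only. It assumes a safety set of 48 and a participant with no other SAE. It would be tempting to widen the range with the 34 patients (13 + 21) in Protocol 1.3.3, but that is a count from an August 2017 antithrombin summary and not a safety-set size.

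The point deserves correction because the exposed data serve the primary objective and the repair is small. It is not evidence that SAEs have been missed.

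**What to change.** 1. **Protocol 9.2.1.** Qualify the sentence on bleeding events by adding: unless they meet an SAE criterion in Section 9.2.2, in which case they are also recorded and reported as SAEs under Section 9.2.9. This carries the sponsor's own 8.1 rule into the AE definition. Because it is attached to the wider term used in 9.2.1, it also covers bleeds managed without factor.
2. **Before database lock.** Reconcile the bleeding events page against the AE/SAE records, query any bleed that appears to meet a 9.2.2 criterion but has no SAE entry, and state in SAP 6.8.2 that confirmed cases enter the SAE tables. This can recover events already missed.

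The cost is a wording change at the next amendment, or a site clarification in the meantime, and one data-management check. An amendment needs ethics approval at up to 30 centers, so the wording is best bundled with other changes. The reconciliation protects the analysis without waiting for it. No patient procedure changes.
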